5.2.3. Other Efficacy Assessments

The efficacy assessments of Items 3, 4, 5 and 8 of the mRESQ-eD (Table 3), together with the assessments below, are used in determining the additional efficacy parameters.

Other Daily Assessments

- 1. Additional GERD symptom assessments are completed by patients once daily in the evening before bed via eDiary (Table 3):
 - Difficulty swallowing (Item 3 of the mRESQ-eD)
 - Hoarseness (Item 4 of the mRESQ-eD)
 - Cough (Item 5 of the mRESQ-eD)
 - Burping (Item 8 of the mRESQ-eD)
- 2. Assessment of sleep disturbance due to GERD symptoms (Daily Sleep Disturbance due to GERD [Table 3]) are completed by patients once daily upon getting up each morning via eDiary:
 - Last night, did you have trouble falling asleep because of GERD symptoms?
 - Last night, how many times did you wake up during the night because of GERD symptoms?
- 3. Use of per-protocol rescue medicine (Table 3) is completed by patients once daily in the evening before bed via eDiary:
 - How many times did you use your rescue medicine (liquid antacid) during the past 24 hours?

4. Heartburn score is rated by patients once daily in the evening before bed via eDiary (Table 3)

Weekly Assessments

The following information is completed by patients once each week during the evening before bed via eDiary (Table 3):

- 1. Degree of Relief Assessment
- 2. Bothersomeness Assessment
- 3. Treatment Satisfaction Assessment

EGD Assessments

The following information is collected by the review the EGDs, obtained at the times specified in the protocol, according to the Los Angeles Classification of Esophagitis (Table 3):

1. Erosive Esophagitis Healing Assessment

5.3. Health Outcomes Assessments

WPAI-Sleep Disturbance-GERD

The Work Productivity and Activity Impairment Questionnaire: Sleep Disturbance-GERD (WPAI-Sleep-GERD) include questions about time lost from work, reduced productivity while at work, and reduced productivity while doing regular daily activities resulting from sleep disturbance due to GERD symptoms. Patients will complete the WPAI-Sleep-GERD at the Randomization Visit, the Week 4 Visit, and at the EOT Visit and will record their responses in the eDiary.

EQ-5D-3L

The EuroQol (EQ)-5D-3L is a generic measure of health widely used in Europe (2). The first component consists of 5 questions assessing the following dimensions: mobility, self-care, usual activities, pain/discomfort, and anxiety/depression. Responses to the 5 questions define a health state. The second component of the EQ-5D is a visual analogue scale, asking patients to rate their health from 0 to 100 (0 represents worst imaginable health state and 100 represents best imaginable health state). Patients will complete the EQ-5D-3L at the Randomization Visit, the Week 4 Visit, and at the EOT Visit and will record their responses in the eDiary.

5.4. Other Assessments

Esophagogastroduodenoscopy

All patients will be required to undergo an EGD during the Screening Period. There should be a minimum of 7 days between the EGD and the start of the Pretreatment Period to allow for pH testing and patient stabilization. An EGD will be performed at the Week 8/EOT Visit for all patients who have completed at least 4 weeks of treatment and had erosive esophagitis on the screening EGD (based on the Los Angeles Classification of Esophagitis, Appendix 8) as determined by either the site personnel or the central reader.

Baseline EE status is determined using images created during a screening EGD by the local reads. These images are read and interpreted both by local physicians and centrally. There were 3 different approaches to determine the baseline EE status:

- 1. The site coordinator used the web-based reporting system provided by Suvoda to enter the EE information into the Interactive Response Technology (IRT) system. This information was used for randomization.
- 2. The site coordinator entered the local reads into the eCRF.
- 3. Central review: In some cases, the images received by the central reviewers were of poor quality and the central-reviewing physicians were unable to read the images. Thus, as a practical matter, the values were set to missing. The central reads are not used to overturn the local reads, and the central reads are not used anywhere in the study.

The local reads (Item 2 in the list above) of EE status will be used for statistical inference, while the central reads (Item 3 in the list above) will be used for the esophageal erosion healing analysis only.

5.5. Safety Assessments

Safety will be evaluated by AEs and serious adverse events (SAEs), standard clinical laboratory assessments, vital signs, physical examinations, medical and disease history, and electrocardiograms (ECGs). Planned timepoints for all safety assessments are provided in the Schedule of Evaluations (Appendix 4).

5.5.1. Adverse Events

An AE is any untoward medical occurrence associated with the use of a drug in humans, whether or not considered drug related.

An AE, therefore, can be any unfavorable and unintended sign (including an abnormal laboratory finding, for example), symptom, or disease temporally associated with the use of a medicinal product, whether or not considered related to the medicinal product. A procedure is not an AE, but the reason for a procedure may be an AE.

A treatment-emergent adverse event (TEAE) is an event that emerges, or a preexisting event that worsens (with a new start date), any time after administration of the first dose of study drug during the treatment emergent period, which is defined as the date and time of the first treatment to the date and time on or ≤ 1 day of the last treatment. In fact, there is an Investigator assigned flag on the eCRF to indicate an TEAE. The Investigator will provide an assessment of the AE relationship to study drug and AE severity for each AE.

The AE assessment (interview) will be collected from the time the patient signed the informed consent until completion of the Follow-up Phone Call. At each trial visit, the investigator will inquire about the occurrence of AEs/SAEs since the last visit. In addition, certain laboratory abnormalities and changes in vital signs, physical examination findings, and 12-lead ECG parameters are considered AEs per protocol if the Investigator considers them clinically significant and/or they necessitate intervention. These abnormal findings will be captured on the AE page of the electronic case report form (eCRF).

5.5.1.1. Adverse Events Causality Assessment

For all AEs, the investigator must provide an assessment of causal relationship to the study drug. The investigator must assess the relationship of each AE (including SAEs) to the use of a study drug using a 2-category scale (not related or related) based on clinical judgment and using all available information, and may include consideration of the following factors:

- Possible alternative causes of the AE, including the disease under treatment, preexisting conditions, concomitant use of other drugs, and presence of environmental or genetic factors
- The temporal association between drug exposure and onset of the AE
- Whether the manifestations of the AE are consistent with known actions or toxicity of the study drug
- Whether the AE resolved or improved with stopping use of the study drug.
- Judgment should be used if multiple products are discontinued at the same time.

The causality assessment must be recorded in the patient's source documentation and on the AE page of the patient's eCRF. The causal relationship between study drug and the AE will be assessed using the categories shown in the following table:

Category	Definition	
Not related	An AE is not associated with study medication if:	
	- Lack of a temporal relationship to study drug administration makes a causal relationship improbable (eg, the event did not occur within a reasonable time frame following administration of the study medication); and/or	
	- Other causative factor(s) (eg, a preexisting clinical condition, other concomitant treatments) more likely explain the occurrence of the event, and	
	- The event did not improve with stopping of the investigational product, and/or	
	- The event did not recur upon re-exposure with investigational product	
Related	An AE is attributed to the study medication if:	
	- A temporal relationship to study drug administration makes a causal relationship plausible (eg, the event occurred within a reasonable timeframe following administration of study medication); and/or	
	- Other causative factor(s) (eg, the patient's clinical condition, other concomitant treatments) either do not explain the event or are less equally likely to have led to the occurrence of the event, or	
	- The event improved with stopping of the investigational product, and/or	
	- The event recurred upon re-exposure with investigational product	

5.5.1.2. Classification of Adverse Event Severity

The investigator or delegated physician will provide an assessment of the severity of each AE by recording a severity rating in the patient's source documentation and on the AE page of the patient's eCRF. *Severity*, which is a description of the intensity of manifestation of the AE, is distinct from *seriousness*, which implies a patient outcome or AE-required treatment measure

associated with a threat to life or functionality. Severity will be assessed according to the following scale by the investigators:

Mild	A type of AE that is usually transient and may require only minimal treatment or therapeutic intervention. The event does not generally interfere with usual activities of daily living.
Moderate	A type of AE that is usually alleviated with additional specific therapeutic intervention. The event interferes with usual activities of daily living, causing discomfort, but poses no significant or permanent risk of harm to the research participant.
Severe	A type of AE that interrupts usual activities of daily living, or significantly affects clinical status, or may require intensive therapeutic intervention.

AEs should be recorded using the maximum intensity of the event (eg, if a patient reported nausea lasting 3 days, 1 start date and 1 stop date should be recorded along with the maximum intensity experienced for that event over that 3-day timeframe).

5.5.1.3. Serious Adverse Events

All adverse events will be categorized as Serious or Non-Serious. An AE is considered "serious" if, in the view of either the Investigator or Sponsor, it results in any of the following outcomes:

- Death
- Life-threatening experience
- Inpatient hospitalization or prolongation of existing hospitalization
- A persistent or significant disability/incapacity or substantial disruption of the ability to conduct normal life functions
- A congenital anomaly or birth defect

Is considered an important medical event: It may not result in death, be life-threatening, or require hospitalization may be considered serious when, based upon appropriate medical judgment, they may jeopardize the subject and may require medical or surgical intervention to prevent one of the outcomes listed in this definition.

5.5.2. Medical and Disease History

A complete medical and disease history will be performed as defined in the Schedule of Evaluations (Appendix 4).

5.5.3. Physical Examination, Body Weight, and Height

A complete physical examination will be performed as defined in the Schedule of Evaluations (Appendix 4). A physical examination will include the following assessments: general appearance; head, ears, eyes, nose, and throat (HEENT); cardiovascular system; neck; respiratory system; musculoskeletal system; abdomen/liver/spleen; skin; lymph nodes; mental status; and neurologic status. Breast, genitourinary, and rectal examinations are optional at the discretion of the investigator.

Each patient's weight will be recorded at every study visit; height will only be recorded at the Screening Visit.

5.5.4. Vital Signs

Vital sign measurements will be performed as defined in the Schedule of Evaluations (Appendix 4). Respiratory rate, pulse, and blood pressure readings will be taken after the patient has been seated for at least 5 minutes.

5.5.5. Electrocardiograms

A 12-lead ECG will be performed as defined in the Schedule of Evaluations (Appendix 4). ECGs should be obtained after the patient has been supine for at least 5 minutes.

5.5.6. Clinical Laboratory Data

Blood and urine samples for clinical laboratory tests will be collected at the visits defined in the Schedule of Evaluations (Appendix 4). The clinical laboratory tests for hematology, chemistry, urinalysis, coagulation, pregnancy test and drug screening will be performed. For details refer to Clinical Study Protocol C3718-301, Section 3.5.6.

6. STATISTICAL METHODS

6.1. General Methods

In general, descriptive statistics will be presented by treatment group and by visit, as applicable. Descriptive statistics including the number of patients, mean, standard deviation (SD), median, minimum, and maximum will be calculated for continuous variables. Frequencies and percentages for each category will be calculated for categorical variables. All hypothesis tests will be 2-sided with a 5% significance level, and 95% confidence intervals (CIs) will be used.

Baseline EE status (EE vs. non-EE) that is based on local reader's assessments using images created during a screening EGD, and baseline WHSS (<3 vs. ≥3) per eDiary assessments by mRESQ-ed questionnaire are used for analysis, whenever it is appropriate.

All statistical analyses will be performed using SAS Version 9.4 (or later).

6.2. Adjusting for Baseline Characteristics and Covariates

Analyses of efficacy parameters will be adjusted by randomization stratification variables baseline EE status (EE vs. non-EE) and baseline WHSS ($\leq 3 \text{ vs.} \geq 3$).

As a general approach, the baseline value will be included in the linear mixed effects-model for repeated measures (MMRM) and Poisson model analysis as a covariate when the postbaseline or change from baseline values are analyzed, and the randomization stratification variables baseline EE status and baseline WHSS ($<3 \text{ vs.} \geq 3$) will be adjusted in the analysis model as well. Heterogeneity of slopes will be explored, when appropriate.

6.3. Handling of Dropouts/Missing Data Imputation Method

The WHSS (Section 7.9.1.2) is the average of non-missing Daily Heartburn Severity Scores (DHSS) for the week (Appendix 1). If a patient who reported DHSS for fewer than 1 day during a week within the Treatment Period for a given week, then WHSS is missing for that week.

The WRFS (Section 7.9.2) for a week is the average of the non-missing Daily Regurgitation Frequency Scores (DRFS) for that week (Appendix 1). If a patient who reported DRFS for fewer than 1 day during a week within the Treatment Period for a week, then WRFS is missing for the week.

For responder parameters, OHR (Section 7.9.2), a patient who reported daily symptom severity scores for fewer than 4 days during a week within the Treatment Period will be considered a non-responder for that week. A patient will be deemed a weekly non-responder for all weeks following the patient's discontinuation from the study.

Unless stated otherwise, missing data will not be imputed for any of the efficacy parameters.

6.4. Interim Analysis and Data Monitoring

No interim analyses are planned to compare treatment groups with respect to efficacy or safety prior to formal completion of the trial.

6.5. Multicenter Studies

This study is being conducted in approximately 100 centers. For reporting purpose, study centers will be pooled into the following 6 geographic regions (as listed in Appendix 3): US Northeast, US Southeast, US Southeast, US Southeast, US West and Canada.

6.6. Multiple Comparisons/Multiplicity

The overall family-wise Type I error rate for the primary and key secondary efficacy analyses will be controlled at the $\alpha = 5\%$ level by employing a fixed sequence testing method. If the primary hypothesis for the comparison between the placebo group and the IW-3718 group is statistically significant ($\alpha < 5\%$) in the mITT Population (defined in Section 7.1), then the primary objective of the trial will have been achieved and the next hypothesis can be tested; otherwise, testing will stop. The testing of each subsequent hypothesis is conditioned upon all the previous hypotheses being rejected at the 5% level of significance. If a hypothesis is not rejected at the 5% level of significant.

Testing Order	Parameters
1	Change from Baseline in WHSS at Visit 5 (Week 8)
2	Change from Baseline in WRFS at Visit 5 (Week 8)
3	Overall Heartburn Responders
4	Proportion of Heartburn-free Days During the 8-week Treatment Period

Table 4: Testing Order of Efficacy Parameters for the Fixed Sequence Testing

6.7. Examination of Subgroups

Subgroup analyses will be performed on the primary efficacy parameter, using the subgroups defined in Table 5.

Table 5:Subgroup Variables

Subgroup Variables	Subgroups
Age (years)	18 to <40; 40 to <65; \geq 65
Sex	Female; Male
Race	Caucasian; Black/African American; Other
Ethnic Origin	Hispanic; Non-Hispanic
Body Mass Index (BMI)	$<30 \text{ kg/m}^2; \ge 30 \text{ kg/m}^2$
Baseline EE Status	EE; non-EE
Baseline WHSS	<3;≥3

7. ANALYSIS METHODS

7.1. Analysis Populations

- Screened Population consists of all patients who signed informed consent and received a patient identification (PID) number.
- **Randomized Population** consists of all patients who were assigned to a treatment group (placebo or IW-3718) via randomization.
- **Final Efficacy Analysis Randomized Population** consists of all patients who were randomized prior to or on August 4, 2020.
- **Safety Population** consists of all randomized patients who received at least 1 dose of study drug. Safety analysis will be based on the Safety Population, in which patients are evaluated according to the treatment they received.
- **Modified Intent-to-Treat (mITT) Population** consists of all patients who were randomized prior to or on August 4, 2020, and who received at least 1 dose of study drug and had at least 1 postbaseline primary efficacy assessment. This population will be used for the final efficacy analysis.
- Sensitivity Analysis (SA) Population consists of all randomized patients who received at least 1 dose of study drug and had at least 1 postbaseline primary efficacy assessment. This population will be used for the efficacy sensitivity analysis at completion of the study.

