Clinical Study Protocol: C3718-301

Amendment 2, 14 August 2020

Study Title:	A Phase 3, Randomized, Double-blind, Placebo-controlled, Parallel-group, Multicenter Trial of Oral IW-3718 Administered to Patients with Gastroesophageal Reflux Disease while receiving Proton Pump Inhibitors
Study Number:	C3718-301
Study Phase:	3
Product Name:	IW-3718
Indication:	IW-3718 is indicated as an adjunct to proton pump inhibitors to treat persistent (also referred to as refractory) gastroesophageal reflux disease symptoms such as heartburn and regurgitation that are not resolved with proton pump inhibitor therapy alone.
Sponsor:	Ironwood Pharmaceuticals, Inc. [name]
Sponsor Contact:	
Medical Monitor:	

	Date
Original Protocol:	15 March 2018
Amendment #1	23 June 2018
Amendment #2	14 August 2020

Confidentiality Statement

The contents of this document are confidential and belong to Ironwood Pharmaceuticals, Inc. Except as may be otherwise agreed to in writing, by accepting or reviewing these materials, you (including any colleagues or subordinates) agree to hold such information in confidence and not to disclose it to others (except where required by applicable law), nor to use it for unauthorized purposes. In the event of actual or suspected breach of this obligation, Ironwood should be promptly notified.

SYNOPSIS

Study Number: C3718-301

Study Title: A Phase 3, Randomized, Double-blind, Placebo-controlled, Parallel-group, Multicenter Trial of Oral IW-3718 Administered to Patients with Gastroesophageal Reflux Disease while receiving Proton Pump Inhibitors

[figure not shown]
Study Centers: Approximately 100 centers in the United States and Canada

Development Phase: 3

Objectives: The objective of this study is to evaluate the safety and efficacy of IW-3718 administered to patients with GERD who continue to have persistent symptoms, such as heartburn and regurgitation, while receiving once-daily (QD), standard-dose proton pump inhibitors (PPIs).

Methodology: This is a multicenter, randomized, double-blind, placebo-controlled, parallel-group, 8-week study, consisting of 4 distinct periods as illustrated in the figure below. The study will enroll patients who have GERD and continue to experience GERD symptoms while receiving QD, standard-dose PPI therapy. Eligible patients will continue to take their PPI and will be randomized to placebo or to 1500 mg IW-3718 BID.

Overview of Study Design

Note: There is no Day 0

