3.7.1 Analysis Populations

Screened Population consists of all patients who signed informed consent and received a patient identification (PID) number.

Randomized Population consists of all patients who were assigned to a treatment group (placebo or IW-3718) via randomization.

Safety Population consists of all randomized patients who received at least 1 dose of study drug.

Modified Intent-to-Treat (mITT) Population consists of all randomized patients who received at least 1 dose of study drug and had at least 1 postbaseline primary efficacy assessment.

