3.4. Assigning Patient to Treatment Group

Patients who meet all the inclusion criteria and none of the exclusion criteria will be randomized into the study at the Randomization Visit on Day 1. Approximately 550 patients will be stratified by 1) whether they have or do not have EE on the screening EGD and 2) their baseline heartburn severity level (<3 vs. \geq 3); and randomized through central randomization in a 1:1 ratio to either 1500-mg IW-3718 BID (while taking their usual label-dose PPI) or placebo BID (while taking their usual label-dose PPI).

The computer-generated randomization schedule was prepared by an independent statistician not otherwise associated with the study. Randomization numbers will be assigned by interactive web response system (IWRS).

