7.2. Patient Disposition

The number and percentage of screen failure patients (ie, patients who entered the Screening Period but not the Pretreatment Period), the number and percentage of pretreatment failures (ie, patients who entered the Pretreatment Period but were not randomized), along with the associated reasons for failure, will be tabulated overall for the Screened Population. Patients who initially failed screening and were re-screened will only be counted once, that is, the PID used for the rescreened patients will be listed for patient disposition, while the PID assigned for the original screening will not be analyzed or listed.

The number and percentage of randomized patients who were included in the Safety Population, who were included in the mITT Population, who completed the Treatment Period, and who prematurely discontinued treatment will be presented overall and by treatment group. A patient is considered to have completed the Treatment Period if the patient completed the 8 weeks of treatment and the EOT Visit that was recorded on the end-of-treatment eCRF page. The reason for premature discontinuation as recorded on the eCRF will also be summarized by treatment group and overall.

The number and percentage of patients who prematurely discontinued treatment will be presented for each treatment group by time of discontinuation, defined as the week (Week 1 through Week 8) in which the treatment discontinuation occurred.

The number of patients screened, the number and percentage of patients randomized will be presented by study center within each geographic region (See Appendix 3 for the definitions of

the geographic regions). A separate disposition table will be generated to include the SA Population and other relevant information.

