7.9. Efficacy Analysis

The final efficacy analysis will be based on the mITT, while the SA Population will be used for the sensitivity efficacy analysis, and the analyses will be conducted according to the treatment assigned. Baseline values for efficacy parameters are defined as:

- For change from baseline continuous parameter and derived dichotomized response variables, the baseline will be derived from the eDiary and/or eCRF data collected for the last week of the Pretreatment Period (or Week -1), specifically the period from 7 days prior to the day of randomization.
- A time dependent proportion efficacy parameter that is defined as days the event of interest occurs, divided by the number of diary entry days during the relevant period. Its baseline period is the last 14 days (Week -2 to Week -1) prior to day of randomization.

For the change from baseline and response variables, if data for Week -1 are not available, data for Week -2 (the second last week of the Pretreatment Period) will be used.

For responder parameters derived from daily eDiary assessments, a patient who missed 4 or more daily assessments an analysis week will be consider a missing for that week and will be defined as a non-responder for that week. For continuous efficacy parameters, the analysis value for an analysis period is defined as the average of the non-missing values during that period (Appendix 1). If a patient who reported assessments for fewer than 1 day during a week within the Treatment Period, the average is missing for that week. For efficacy parameters no further imputation will be performed (see Section 7.9.1.3 for sensitivity analyses employing multiple imputation [MI] methods). Any efficacy assessments measured after the last dose date will not be included for analysis.

All primary and secondary efficacy parameters are listed in Table 4 will be tested in the given order to protect the overall family wide alpha level at 5%. The mITT Population will be used for the final analysis for all efficacy parameters. The SA Population will be used for the efficacy sensitivity analysis that include selected efficacy parameters at completion of the study.

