7.11.2. EQ-5D-3L

Each of the 5 questions assessing mobility, self-care, usual activities, pain/discomfort, and anxiety/depression will be summarized by treatment group and by frequency distribution (profile) of the EQ-5D descriptive system ("No problems", "Some problems", "Extreme problems") at baseline, Week 4 and Week 8. Comparison between treatment groups at Week 8 will be performed utilizing the CMH test, controlling for strata: baseline EE status (present vs. not present), baseline heartburn severity level ($<3 \text{ vs.} \ge 3$) and the associate p-value will be reported. In addition, shift in response to each question from baseline to each visit postbaseline will be summarized using a shift table.

Change from baseline at week 4 and Week 8 in health state as assessed by a 0 to 100 visual analogue scale will be summarized by treatment group and analyzed using a similar MMRM approach described in Section 7.9.1.2.

8. **REFERENCES**

- 1. Statistical Considerations for Clinical Trials During the COVID-19 Public Health Emergency Guidance for Industry, U.S. Department of Health and Human Services Food and Drug Administration (June, 2020)
- 2. EuroQol G. EuroQol--a new facility for the measurement of health-related quality of life. The EuroQol Group. Health Policy. 1990; 16:199-208.
- 3. Newcombe, R. Interval estimation for the difference between independent proportions: Comparison of eleven methods. Stat. Med. 1 998; 17: 873-890.
- 4. Cohen, J. *Statistical power analysis for the behavioral sciences*, Hillsdale, NJ, Lawrence Earlbaum Associates. 1988
- 7. Rubin DB (1987) Multiple Imputation for Nonresponse in Surveys. John Wiley & Sons Ltd., New York.

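### SAP Table 2 gives power for 330 per group, but the SAP also puts the trial at about 550 patients and tests a date-limited mITT of unstated size

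*SAP*

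**What the plan says.** **Population.** Protocol 3.7.1 defines the analysis set without a date: "Modified Intent-to-Treat (mITT) Population consists of all randomized patients who received at least 1 dose of study drug", with at least one postbaseline primary assessment. The protocol version is "Amendment 2, 14 August 2020", and SAP Section 1 names that version as the one it follows. SAP 7.1 keeps the name mITT but adds a cut-off: the population "consists of all patients who were randomized prior to or on August 4, 2020, and who received at least 1 dose of study drug", with the same assessment requirement. The protocol's undated definition reappears in SAP 7.1 as the Sensitivity Analysis (SA) Population.

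**Role.** SAP 6.6 says that if the primary comparison is significant "in the mITT Population (defined in Section 7.1), then the primary objective of the trial will have been achieved". SAP 7.9 adds: "The mITT Population will be used for the final analysis for all efficacy parameters". The SA Population has a sensitivity role only.

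**Size.** SAP Section 4 states 660 patients, 330 per group, and Table 2 gives fixed-sequence power of 99/99/99/88% at that size. Protocol 3.3 also gives 660. SAP 3.4 says "Approximately 550 patients will be stratified by" the two randomisation factors and allocated 1:1. Appendix 1 gives about 550 as the size of the current study and runs its missing-data simulations on 550.

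**The concern.** Table 2 is the SAP's only statement of what the confirmatory sequence can be expected to deliver. It is computed for 330 per group. The sequence is tested on patients randomised by 4 August 2020, and elsewhere the same SAP sizes the trial at about 550. A reader cannot learn from Section 4 how many patients carry the tests or with what power.

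The date limit also changes the protocol's primary efficacy population under an unchanged name. The cut-off falls 10 days before Amendment 2, yet that amendment's mITT does not contain it. The SAP, dated 14 January 2021, introduces it without saying that it departs from protocol 3.7.1. What is at stake is the accuracy of a stated power and the traceability of the confirmatory population. The treatment comparison itself is not at stake, because the cut-off applies to both arms alike.

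**Working it through.** **Inputs** (SAP Table 1, placebo vs IW-3718; two-sided alpha 0.05, fixed sequence):

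- WHSS change: -1.58 (SD 1.20) vs -2.01 (SD 1.29), difference 0.43
- WRFS change: -0.81 (SD 1.12) vs -1.26 (SD 0.91), difference 0.45
- Overall Heartburn Responder: 18/49 vs 31/55
- Proportion of heartburn-free days: 0.195 (SD 0.2822) vs 0.268 (SD 0.2928), difference 0.073

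**Method.** Section 4 used t-tests and a chi-square test on bootstrap samples. The patient data are not available, so I used the analytic equivalents.

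- Continuous endpoints: s = √((s₁² + s₂²)/2); noncentrality = difference / (s√(2/n)); power from the noncentral t with 2n - 2 degrees of freedom. The pooled SDs are 1.246, 1.020 and 0.2875.
- Responder: z = [|p₁ - p₂| - 1.96√(2p̄(1 - p̄)/n)] / √([p₁(1 - p₁) + p₂(1 - p₂)]/n); power = Φ(z).
- Fixed-sequence power through step k: the product of the first k marginal powers, treating the endpoints as independent.

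**Step 1: reproduce Table 2 at n = 330.** The noncentralities are 4.434 (WHSS), 5.665 (WRFS) and 3.261 (heartburn-free days); z = 3.157 for the responder. The marginal powers are 99.32, 99.99, 99.92 and 90.26%. The cumulative products are 99.3/99.3/99.2/89.6%, against 99/99/99/88% stated. The first three agree and the fourth is within 2 points of the bootstrap figure. Table 2 is sound for 330 per group.

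**Step 2: the other size in the SAP, 550/2 = 275 per group.** The noncentralities are 4.047, 5.171 and 2.977; z = 2.707. The marginal powers are 98.12, 99.93, 99.66 and 84.42%.

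**Step 3: other sizes.** The mITT size is not stated, so 320, 225 and 200 are assumed sizes that show the range.

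| n per group | Step 1 | Step 2 | Step 3 | Step 4 |
|---|---|---|---|---|
| 330 (Table 2) | 99.3 | 99.3 | 99.2 | 89.6 |
| 320 (assumed) | 99.2 | 99.2 | 99.1 | 88.5 |
| 275 (550 in total) | 98.1 | 98.1 | 97.7 | 82.5 |
| 225 (assumed) | 95.5 | 95.2 | 94.0 | 72.1 |
| 200 (assumed) | 93.1 | 92.4 | 90.4 | 64.8 |

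**Step 4: the independence assumption.** Three of the four endpoints come from the same heartburn items, so their tests are correlated. Simulating correlated test statistics (normal approximation) with a common correlation from 0 to 0.9 moves step 4 from 89.8 to 90.4% at 330 per group, and from 82.7 to 84.5% at 275. Like for like, going from 330 to 275 costs about 6 to 7 points at step 4 and about 1 point on the primary.

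**Step 5: which row applies.** The documents allow three readings of 550:

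- It is the set randomised by the cut-off. The 275 row then applies, before the dose and assessment requirements.
- It is the whole trial. The mITT is then below 275 per group if anyone was randomised after 4 August 2020.
- It misstates 660. The mITT then lies below 330 by the number randomised after the date; if that number is small, something like the 320 row applies.

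**The case against.** The strongest case on the other side has four parts.

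- **Section 4 is a design rationale.** It says why 660 was chosen, states its n and calculates it correctly. That stands as to the arithmetic. It does not settle the conflict with 550 in two other places, or say what power the tested population has.
- **The restriction is open and its role is clear.** SAP 7.1 states the date and also defines a separate randomised population for the same cut-off. SAP 6.6 and 7.9 give the confirmatory tests to the mITT and sensitivity to the SA Population. This stands. A reader might infer that it is unclear which result governs, or that the primary population must be switched back; the text does not support either inference.
- **The counts will be reported anyway.** SAP 7.2 tabulates the mITT and adds: "A separate disposition table will be generated to include the SA Population and other relevant information". That is true, but those figures come with the results and do not correct the planning statement.
- **A reason may exist.** SAP Section 8 lists "Statistical Considerations for Clinical Trials During the COVID-19 Public Health Emergency Guidance for Industry". A reader might infer that the pandemic explains the date, but no text available for this review links the two. The opening part of the SAP was not available, so the absence of an explanation or change label is judged on the rest.

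Two stronger readings also fail. One is that 550 is the size of the mITT; the documents never say so. The other is that the trial is underpowered for its primary endpoint; even 200 per group leaves about 93% on the sponsor's assumptions.

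**Conclusion.** The point holds as an inconsistency in the SAP. It states two sample sizes for one trial, and its only power table is not tied to the date-limited population that carries the confirmatory sequence. That population departs from protocol 3.7.1 without being identified as doing so.

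The size of the effect depends on a number the documents do not give. At 275 per group the primary keeps about 98% and step 4 is about 82-83%, against 88% stated and 89.6% reproduced at 330. It would be wrong to say that the loss is confined to the fourth test: if 550 is the whole trial and the cut-off removes patients, the primary falls too, for example to 95.5% at an assumed 225 per group, with 72% at step 4. Equally, if 550 is a misstatement and few patients came after the date, Table 2 is close to right.

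These figures take the Phase 2b estimates in Table 1 as true and treat the endpoints as independent. They are t-test and chi-square powers, as in Table 2, and not those of the planned MMRM, CMH and Poisson or negative binomial analyses. Nothing here suggests bias or a data-driven choice of date.

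**What to change.** Before unblinding:

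1. Use one sample size in SAP 3.4, Section 4 and Appendix 1, or state what each number refers to.
2. Rerun the sponsor's existing bootstrap and restate Table 2 for the patients randomised by 4 August 2020 who make up the mITT, giving that number. The analytic figures above show the scale and should not replace the bootstrap.
3. Identify the date limit in SAP 7.1 as a departure from protocol 3.7.1. A sentence giving the reason would help the reader.

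No change of primary population and no new rule on which result governs is needed.

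The cost is one simulation rerun, a few lines of SAP text, and a stated power that may look less favourable, mainly at step 4. No further patients are needed. Enrolment into the cut-off set had closed 163 days before the SAP's date, so the count can be obtained without treatment codes.
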